## Follicle-Stimulating Hormone (FSH)

Follicle-stimulating hormone (FSH) should be tested at Screening if the female subject is  $\leq 55$  years of age AND has had no menses for  $\geq 12$  months AND has no history of permanent surgical sterilization.

## Clinical Chemistry

Blood samples will be collected following a minimum 8-hour fast for the Baseline visit (i.e., for lipid testing). If a subject is not able to fast at this visit, due to unforeseen circumstances, the non-fasting status will be recorded in study source documentation and lab requisition. Blood samples at other visits can be drawn without prior fast.

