## APPENDIX D. ACTIVITY SCHEDULE

The following table shows the required activities across the Screening and subsequent study visits. The individual activities and allowed modifications due to COVID 19 are described in detail in the Operations Manual ([Appendix F](#)).

Study Activities Table

Activity	Day -35 to Day -1	Day 0	Day 14 (± 3 Days)	Day 28 (± 3 Days)	Day 70 (± 3 Days)	Day 112 (± 3 Days)	Day 140 (± 7 Days)	Day 168 (± 7 Days)	Day 196 (± 7 Days)	Day 280 (± 7 Days)	Day 365 (± 7 Days)	20 Weeks After Last Dose	Follow Up Call
Subject information and informed consent (and assent, where applicable)	✓												
Eligibility criteria	✓	✓											
Medical history	✓	✓											
Atopic dermatitis history	✓	✓											
Asthma symptoms (if applicable, using Asthma Control Questionnaire-5 [ACQ-5])		✓											
Demographics	✓												
Drug, tobacco (including e-cigarettes), and alcohol history	✓												
Adverse event assessment	✓	✓	✓	✓	✓	✓	✓	✓	✓	✓	✓	✓	✓
Prior/concomitant therapy	✓	✓	✓	✓	✓	✓	✓	✓	✓	✓	✓	✓	✓
TB screening	✓												
Investigator assessments (EASI, BSA, vIGA-AD)	✓	✓	✓	✓	✓	✓	✓	✓	✓	✓	✓	✓	✓
Investigator assessment (SCORAD)		✓		✓		✓			✓		✓		
Patient reported outcomes (Worst Pruritus NRS, ADerm-SS, and ADerm-IS)	✓	✓	✓	✓	✓	✓			✓	✓	✓	✓	✓
Patient reported outcomes (DLOI/CDLOI, POEM)		✓		✓		✓			✓	✓	✓	✓	✓

Activity	Screening Day -35 to Day -1	Baseline/Week 0 Day 0	Week 2 Day 14 (± 3 Days)	Week 4 Day 28 (± 3 Days)	Week 10 Day 70 (± 3 Days)	Week 16 Day 112 (± 3 Days)	Week 20 Day 140 (± 7 Days)	Week 24 Day 168 (± 7 Days)	Week 28 Day 196 (± 7 Days)	Week 40 Day 280 (± 7 Days)	Week 52/PD Day 365 (± 7 Days)	Follow Up Call 20 Weeks After Last Dose
Patient reported outcome (PGIS)		✓	✓	✓	✓	✓			✓	✓	✓	
Patient reported outcome (PGIC)			✓	✓	✓	✓			✓	✓	✓	
EQ-5D-5L, SCORAD (subject-reported items)		✓		✓		✓			✓	✓	✓	
12-lead ECG	✓											
Height (Screening only), weight, and waist circumference (adults)	✓										✓	
Height, weight, and waist circumference (of adolescent age at Baseline)	✓		✓						✓		✓	
Vital signs	✓	✓	✓	✓	✓	✓	✓		✓	✓	✓	
Physical examination	✓	✓									✓	
FSH, serum pregnancy test at central laboratory	✓											
Urine pregnancy test (local)		✓		✓		✓	✓		✓	✓	✓	
Central laboratory tests – Hematology and clinical chemistry	✓	✓	✓	✓	✓	✓	✓		✓	✓	✓	
Central laboratory tests – Total cholesterol, high-density lipoprotein cholesterol (HDL-C), low-density lipoprotein cholesterol (LDL-C), triglycerides		✓										

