### 3.12 Clinical Laboratory Tests

A certified laboratory will be utilized to process and provide results for the clinical laboratory tests. Laboratory reference ranges will be obtained prior to the initiation of the study. The baseline laboratory test results for clinical assessment for a particular test will be defined as the last measurement prior to the initial dose of study drug.

Instructions regarding the collection, processing, and shipping of these samples will be provided by the central laboratory.

If a laboratory test value is outside the reference range and the investigator considers the laboratory result to be clinically significant, the investigator will:

- repeat the test to verify the out-of-range value;
- follow the out-of-range value to a satisfactory clinical resolution; or
- discontinue the subject from the study or require the subject to receive treatment; in this case, the laboratory result will be recorded as an adverse event.

Clinical Laboratory Tests		
HEMATOLOGY	CLINICAL CHEMISTRY	URINALYSIS
Hematocrit Hemoglobin Red Blood Cell (RBC) count/ Erythrocytes Mean Corpuscular Volume (MCV) White Blood Cell (WBC) count/ Leukocytes Platelet count/Thrombocytes Diff. Automatic (absolute count): Neutrophils Eosinophils Basophils Monocytes Lymphocytes Manual Differential (ONLY IF Automated Differential is abnormal): Neutrophils, bands (Stabs) Neutrophils, polymorphonuclear Eosinophils Basophils Monocytes Lymphocytes	Electrolytes Calcium Sodium Potassium Chloride Bicarbonate Substrates Glucose Blood urea nitrogen (BUN) Creatinine Estimated glomerular filtration rate (eGFR) Bilirubin Total Bilirubin Direct (if total is elevated) Bilirubin Indirect (if total is elevated) Albumin High-sensitivity C-Reactive Protein (hsCRP) Cholesterol, total a LDL Cholesterol a HDL Cholesterol a Triglycerides a FSH b	Dipstick Urinalysis Urine Nitrite Urine Protein Urine Glucose Urine Ketone Urobilinogen Urine Bilirubin Urine RBC/Erythrocytes Urine WBC/Leukocytes Urine pH Urine creatinine Urine Sediment (microscopic examination, only if urine analysis abnormal) Urine Sediment Bacteria Urine Cast in Sediment Urine Squamous Epithelial Cells Urine Sediment Crystals, Unspecified Urine Sediment RBC/Erythrocytes Urine Sediment WBC/Leukocytes Urine Urine Albumin-to-Creatinine Ratio (UACR)

Clinical Laboratory Tests		

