Coagulation: International Normalized Ratio (INR) c	Enzymes Alanine aminotransferase (ALT) Aspartate aminotransferase (AST) Alkaline Phosphatase (AP) Gamma-glutamyl transferase (GGT/ $\gamma$ -GT) Creatine Kinase (CK) Only if CK is elevated: Troponin (point-of-care) OR Troponin (central lab) + CK-MB	
INFECTION SCREENING		PREGNANCY TESTINGe
Hepatitis B surface antigen (HBs Ag) (qualitative) d Hepatitis B surface antibody (HBs Ab) (qualitative) d Anti-Hepatitis B core (HBc) total (qualitative) d Hepatitis B Virus (HBV) DNA (quantitative) d Anti-Hepatitis C Virus (HCV) (qualitative) d HCV RNA (quantitative) d HIV 1 and HIV-2 Ab (qualitative) d QuantiFERON ® -TB (or Interferon gamma release assay [IGRA] equivalent) and/or purified protein derivative (PPD)		Urine Pregnancy test (local) f Serum Pregnancy test g
		PK/IMMUNOGENICITY
	ADDITIONAL TESTING	Serum risankizumab concentration Serum ADA Serum nAb
	IgE	ANAPHYLAXIS TESTINGh
		Serum risankizumab concentration i ADA i nAb i Tryptase j Histamine

- Performed only at Baseline visit (following a minimum 8-hour fast).
- FSH testing is to be done at Screening in all women aged  $\leq 55$  years with no menses for 12 or more months without an alternative medical cause.
- INR test only performed if ALT or AST  $> 3 \times$  ULN (upper limit of normal).
- Performed only at Screening.
- Pregnancy testing is not required for female subjects of non-childbearing potential (defined in protocol).
- Urine pregnancy test will be performed at every dosing visit and the Week 52/PD Visit and must be conducted prior to study drug dosing. Negative urine pregnancy test results must be confirmed prior to study drug dosing.
- Serum pregnancy test is conducted at Screening and at other visits only if urine pregnancy test is positive. Negative serum pregnancy test results must be confirmed prior to study drug dosing.
- Only performed in case of a suspected anaphylactic reaction.
- PK and ADA/nAb samples drawn in context of a suspected anaphylactic reaction are collected in addition to those collected at scheduled time points for PK/immunogenicity and are only collected if a suspected anaphylactic reaction occurs while at the study site.

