### 9.3 Analysis of Laboratory Data

Data collected from central and local laboratories, including additional laboratory testing due to an SAE, will be used in all analyses, except for Baseline where SAE-related laboratory assessments on or before the first dose of study drug, or values observed more than 140 days after the last dose of study drug will be excluded. The clinical laboratory tests defined in the protocol operations manual (e.g., hematology and clinical chemistry) will be summarized.

Each laboratory variable will be summarized for all time points (starting with Baseline) with the number of non-missing observations, mean and standard deviation, median, minimum and maximum. Mean change from baseline to each applicable post-baseline visit will be summarized for selected laboratory variables, with the number of observations, baseline mean, and visit mean. The change from baseline mean, standard error, and 95% confidence interval will be presented for the mean change from baseline within each treatment group and difference between treatment groups (risankizumab vs. placebo).

Changes in laboratory parameters will be tabulated using shift tables either by NCI CTC criteria or categorized as low, normal, or high based on the normal ranges of the laboratory used for each sample. A shift table from baseline either to the worst value (based on NCI CTC criteria) during treatment or to minimum and maximum value (based on normal range), will be created. A similar shift table will be provided to summarize shifts from baseline to the final post-baseline value.

Laboratory abnormalities meeting CTC criteria grade 3 and 4 will be summarized.

Laboratory abnormalities will be evaluated based on potentially clinically significant (PCS) criteria ([Appendix C](#)). For each laboratory PCS criterion, the number and percentage of subjects who have a laboratory value meeting the criteria will be summarized. Listings will be provided to summarize subject-level laboratory data for subjects meeting PCI criteria.

Additional summaries will be presented for liver function tests including ALT/SGPT, AST/SGOT, alkaline phosphatase, and total bilirubin, with laboratory values to be categorized as follows:

- $< 1.5 \times \text{ULN}$
- $\geq 1.5 \times \text{ULN} - < 3.0 \times \text{ULN}$
- $\geq 3.0 \times \text{ULN} - < 5.0 \times \text{ULN}$
- $\geq 5.0 \times \text{ULN} - < 10.0 \times \text{ULN}$
- $\geq 10.0 \times \text{ULN} - < 20.0 \times \text{ULN}$

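### Glucose has a fasted baseline and unrestricted follow-up, so its shift tables and within-group changes can rise without a drug effect (minor)

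*Protocol*

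**What the plan says.** The fasting rule is in the Operations Manual (Protocol Appendix F), Section 3.12, Clinical Chemistry: "Blood samples will be collected following a minimum 8-hour fast for the Baseline visit (i.e., for lipid testing". The same paragraph ends: "Blood samples at other visits can be drawn without prior fast". If a subject cannot fast at Baseline, "the non-fasting status will be recorded in study source documentation and lab requisition". Nothing comparable is stated for later visits.

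The laboratory baseline for a test "will be defined as the last measurement prior to the initial dose of study drug" (Section 3.12). The chemistry list includes "Glucose Blood urea nitrogen (BUN) Creatinine", and glucose does not carry the footnote attached to the four lipids: "Performed only at Baseline visit (following a minimum 8-hour fast".

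The Activity Schedule (Protocol Appendix D) has a row "Central laboratory tests – Hematology and clinical chemistry". With the visit lists in Operations Manual Section 2, it places chemistry at Screening, Baseline and Weeks 2, 4, 10, 16, 20, 28, 40 and 52.

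SAP 9.3 plans three outputs that use the baseline value:

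- Mean change, for a selected set of variables that it does not name. "The change from baseline mean, standard error, and 95% confidence interval will be presented for the mean change from baseline within each treatment group", together with the difference from placebo.
- Shift tables from baseline to the worst value, or to the minimum and maximum.
- Shift tables from baseline to the final value.

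It says nothing about fasting status.

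**The concern.** Post-dose glucose may be measured under different conditions from the baseline it is compared with. Eating before a draw would, if anything, raise a later value against a fasted one, so the mismatch pushes in one direction and does not average out.

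The randomised comparison in Period A deals with this, because all arms follow the same sampling rule under the blind. Other outputs lack that protection. From Week 16 every continuing subject receives risankizumab (Protocol 4.1), so Period B has no placebo column. The all-risankizumab population has none either, and SAP 9.1 has it analysed already at Week 16. In those tables a food effect and a drug effect would look alike. Because fasting status is recorded only for a non-fasted Baseline sample, the two could not be separated afterwards.

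**Working it through.** The plan states no figure on this point, so there is none to reproduce. The first two steps are a document check. The third is an illustration on assumed inputs.

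**1. Which tests are affected.** Lipids are scheduled only at Baseline, so they have no later scheduled sample to be mismatched with. Glucose is drawn under the fast on Day 0 and then at eight scheduled visits with no fast required: four in Period A (Weeks 2, 4, 10, 16) and four in Period B (Weeks 20, 28, 40, 52). The Screening draw also falls under the no-fast rule.

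**2. Which outputs are affected.** In SAP 9.3 the shift-table sentence covers laboratory parameters generally, so as written it reaches glucose. Mean change is limited to selected variables, and glucose is not named, so it is affected only if chosen.

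**3. Possible size with no drug effect.** Assumptions, none of them from the documents:

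- fasting mean 5.2 mmol/L, between-subject SD 0.45, within-subject SD 0.3, upper limit of normal 5.9;
- a meal adds max(0, N(D, 0.8D)), with D from 0.3 to 1.0 mmol/L;
- a share f of later samples follows a meal.

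With Φ(1.25) = 0.8944 and φ(1.25) = 0.1826:

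- mean meal rise = D(0.8944 + 0.8 × 0.1826) = 1.040D
- second moment = D²(1.64 × 0.8944 + 0.8 × 0.1826) = 1.613D²
- mean change = 1.040fD
- SD of change = √(2 × 0.3² + 1.613fD² − (1.040fD)²)
- 95% CI half-width for one dose arm of 62 = 2.00 × SD / √62

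Example, D = 0.3 and f = 0.5: mean change 0.156; SD = √(0.180 + 0.0726 − 0.0243) = 0.48; half-width = 2.00 × 0.478 / 7.874 = 0.121.

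The last column is from simulation (124 risankizumab, 31 placebo, highest of the four Period A samples). It agreed within 1 percentage point between arms.

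| Share fed | D (mmol/L) | Mean change | SD of change | CI half-width, n = 62 | Normal-to-high shift on maximum |
|---|---|---|---|---|---|
| 0 | any | 0.00 | 0.42 | 0.108 | about 15% |
| 50% | 0.3 | 0.16 | 0.48 | 0.121 | 33% |
| 50% | 0.6 | 0.31 | 0.61 | 0.155 | 57% |
| 50% | 1.0 | 0.52 | 0.85 | 0.215 | 76% |
| 100% | 0.3 | 0.31 | 0.48 | 0.121 | 45% |
| 100% | 0.6 | 0.62 | 0.61 | 0.155 | 77% |
| 100% | 1.0 | 1.04 | 0.84 | 0.214 | 94% |

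In each row with half or all samples fed, the mean change exceeds the half-width, so a typical within-arm interval would lie above zero with no drug effect. The 15% in the first row is not a food effect. It comes from setting the highest of four values against a single baseline, so only the excess over 15% belongs to eating.

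**4. Period A difference.** The simulated risankizumab-minus-placebo difference in Week 16 change averaged at most 0.006 mmol/L in absolute value in any scenario. The cost is noise: its standard error is SD × √(1/124 + 1/31) = 0.201 × SD, which runs from 0.201 × 0.42 = 0.08 to 0.201 × 0.85 = 0.17.

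**5. Potentially clinically significant flags.** The high limit in SAP Table C-2 is 13.9 mmol/L. No scenario produced a value above it.

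**The case against.** The strongest reply is that the documents do not establish a rise. Later samples may be drawn without a fast, which is a permission and not an instruction to eat. Some Baseline samples may themselves be non-fasted, and no document gives the share of later samples taken after food. With a share of zero the effect is zero. This stands. A reader might infer that the tables will show a rise and that it will be taken for a drug effect; the documents support only that they can show one.

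A reader might also argue that glucose must be in the mean-change analysis because Table C-2 sets limits for it. That does not follow. Table C-2 also lists triglycerides and total cholesterol, which have no scheduled post-baseline sample, so a listing there does not show that change from baseline is planned.

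Third, the Period A placebo columns would show the same shift and give Period B readers an in-trial reference for its size. That is true and reduces the harm, but the reader has to know to look, and nothing in SAP 9.3 says so. It is also a reference from Weeks 2 to 16, not a concurrent control.

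Finally, these are descriptive tables, and glucose is not an area of safety interest in Protocol Table 2 or SAP Appendix B. That stands and sets the severity.

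**Conclusion.** The mismatch is real and the SAP does not address it. Glucose shift tables, and within-group mean change if glucose is selected for that summary, compare a fasted baseline with unrestricted follow-up and can rise with no drug effect. The exposed outputs are the within-group summaries, above all those for Period B and the all-risankizumab population, which have no concurrent placebo.

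The size cannot be fixed from the documents. The figures above rest wholly on the assumed glucose distribution, meal effect and fed share, and they include no effect at all. The Period A risankizumab-minus-placebo difference is not systematically biased. The primary and key secondary endpoints, alpha and sample size are unaffected. This is a minor point about how safety tables can be read.

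**What to change.** In SAP 9.3, keep the Day 0 baseline and all planned tables, and add three things for glucose:

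1. A supplementary change and shift table with the Screening chemistry value as the reference. That sample is already collected under the same no-fast rule as the later visits.
2. A statement that interpretation of glucose rests on the Period A difference from placebo.
3. A label on the Period B and all-risankizumab glucose tables: fasted baseline against unrestricted follow-up, no concurrent control.

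The cost is a few sentences, one extra reference flag and one extra table. No new samples are needed.

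The Screening value should supplement the baseline, not replace it. Replacement would contradict the baseline definition in Operations Manual 3.12. The Screening value can also be up to 35 days old, and in some subjects it may precede washout of systemic corticosteroids, which can affect glucose. Eligibility criterion 29 excludes such exposure within 4 weeks (28 days) before Baseline, and Protocol 5.4 requires consent before a prohibited medication is stopped for the study. That possibility is therefore confined to Screening samples taken in roughly the first 35 − 28 = 7 days of the window. Dropping the Period B or all-risankizumab glucose tables is not advised: it would lose safety reporting where a label is enough.

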## Urinalysis

[figure not shown]
Dipstick urinalysis will be completed by the central laboratory at the Screening visit. Specified abnormal macroscopic urinalyses, defined as leukocytes, nitrite, protein, ketones, blood greater than negative, or glucose greater than normal, will be followed-up with a microscopic analysis at the central laboratory.

### Hepatitis B and C Testing

All subjects will be tested for the presence of the Hepatitis B Virus (HBV) and Hepatitis C Virus (HCV) at Screening. Subjects with Hepatitis B (HBs Ag positive [+] or detected sensitivity on the HBV DNA PCR qualitative test) or Hepatitis C (HCV RNA detectable in any subject with anti-HCV Ab) will be excluded. Subjects who have been vaccinated against Hepatitis B and are HBs Ab positive may be enrolled. If HBs Ag is negative but Hepatitis B core antibodies total is positive, Hepatitis B virus DNA will be quantified. If Hepatitis B virus DNA level is undetectable at Screening, the subject can participate in this study. If Hepatitis C virus antibodies level is positive, Hepatitis C virus RNA will be quantified. If Hepatitis C RNA level is undetectable at Screening, the subject can participate in this study.

Where mandated by local requirements; subjects with HBs Ab+ and/or HBc Ab+ and negative HBV DNA at screening should have HBV DNA PCR testing performed every 12 weeks (q12w). HBV DNA PCR testing q12w is not necessary when the subject has a history of HBV vaccine and is HBs Ab+ and HBc Ab-.

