Central laboratory tests – TB screen (QuantiferON-TB Gold test [or IGRA equivalent] and/or local purified protein derivative [PPD] skin test)	✓										✓	

Activity	Day -35 to Day -1	Day 0	Day 14 (± 3 Days)	Day 28 (± 3 Days)	Day 70 (± 3 Days)	Day 112 (± 3 Days)	Day 140 (± 7 Days)	Day 168 (± 7 Days)	Day 196 (± 7 Days)	Day 280 (± 7 Days)	Day 365 (± 7 Days)	20 Weeks After Last Dose
Central laboratory tests – HIV screening, Hepatitis B and C screening, urinalysis	✓	✓										
Central laboratory test - IgE levels		✓				✓					✓	
Blood samples for risankizumab ADA assay and nAb assay		✓		✓		✓					✓	
Blood samples for risankizumab PK assay		✓		✓		✓					✓	
In-clinic post-dose monitoring for hypersensitivity reactions		✓		✓		✓				✓		
Randomization/drug assignment (for placebo subjects only at Week 16)		✓				✓						
Dispense handheld ePRO device	✓											
Collect handheld ePRO device						✓						
Optional Biomarker Samples (to be Collected Only if Subject Provides Consent)												
Whole blood pharmacogenetic (PG-DNA) (if not collected at Baseline, may be collected at Week 2, Week 4, Week 16, or at the Week 52/PD Visit)		✓										
Whole blood transcriptomic (PG-RNA)		✓		✓		✓					✓	
Whole blood plasma		✓		✓		✓					✓	
Whole blood serum		✓		✓		✓					✓	
Biopsy – Lesional skin punch		✓		✓		✓					✓	
Biopsy – Non-lesional skin punch		✓		✓		✓					✓	

Activity	Day -35 to Day -1	Day 0	Day 14 (± 3 Days)	Day 28 (± 3 Days)	Day 70 (± 3 Days)	Day 112 (± 3 Days)	Day 140 (± 7 Days)	Day 168 (± 7 Days)	Day 196 (± 7 Days)	Day 280 (± 7 Days)	Day 365 (± 7 Days)	20 Weeks After Last Dose
Screening		✓		✓		✓					✓	
Baseline/Week 0		✓										
Week 2												
Week 4				✓								
Week 10												
Week 16						✓						
Week 20												
Week 24												
Week 28												
Week 40												
Week 52/PD												
Follow Up Call												

Note: Column headers in underlined italic font style denote dosing visit.

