#### SCREENING:

 INTERVIEW	
 
• Subject information and informed consent (and assent, where applicable)
 
• Eligibility criteria
 
• Medical history
 
• Atopic dermatitis (AD) history
 
	
 
• Demographics
 
• Drug, tobacco (including e-cigarettes), and alcohol history
 
• Prior/concomitant therapy
 
• Tuberculosis (TB) screening
 

 PRO	
 
• Dispense handheld electronic patient-reported outcome (PRO) device for initiation of daily data collection (if applicable)
 
• Worst Pruritus Numerical Rating Scale (NRS)
 
	
 
• Atopic Dermatitis Symptom Scale (ADerm-SS)
 
• Atopic Dermatitis Impact Scale (ADerm-IS)
 

 EXAM	
 
• Eczema Area and Severity Index (EASI)
 
• Body surface area (BSA)
 
• Validated Investigator Global Assessment Scale for Atopic Dermatitis (vIGA-AD)
 
• Adverse event (AE) assessment
 
	
 
• 12-lead electrocardiogram (ECG)
 
• Height, weight, and waist circumference
 
• Vital signs
 
• Physical examination
 

 CENTRAL LAB	
 
• Follicle-stimulating hormone (FSH) (if applicable)
 
• Serum pregnancy test (for all female subjects of childbearing potential)
 
• Hematology
 
	
 
• Clinical chemistry
 
• TB test
 
• Human immunodeficiency virus (HIV), Hepatitis B and C screening
 
• Urinalysis
 

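### Where local rules mandate it, the text calls for HBV DNA testing every 12 weeks, but the laboratory table says HBV DNA is done at Screening only and no later visit lists it

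*Protocol*

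**What the plan says.** The material is mainly in the Operations Manual (Protocol Appendix F).

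- **Section 3.12, Hepatitis B and C Testing.** The repeat-testing rule opens with its condition and its population: "Where mandated by local requirements; subjects with HBs Ab+ and/or HBc Ab+ and negative HBV DNA at screening". These subjects "should have HBV DNA PCR testing performed every 12 weeks (q12w"). One exemption follows: "HBV DNA PCR testing q12w is not necessary when the subject has a history of HBV vaccine" and is surface-antibody positive and core-antibody negative.
- **Section 3.12, laboratory table, infection-screening block.** The row "Hepatitis B Virus (HBV) DNA (quantitative") carries superscript d. The fourth note under the table, which corresponds to d, reads "Performed only at Screening".
- **Sections 2.1 and 2.2, visit lists.** Screening is the only visit that names hepatitis testing: "Human immunodeficiency virus (HIV), Hepatitis B and C screening". The central-laboratory lists for Baseline and Weeks 2, 4, 10, 16, 20, 28, 40 and 52/PD do not name HBV DNA. Week 24 has no central-laboratory list.
- **Protocol Appendix D, Activity Schedule.** Hepatitis testing sits in one combined row, "Central laboratory tests – HIV screening, Hepatitis B and C screening, urinalysis". That row has no tick after Day 0.
- **Section 5.2, country-specific requirements.** The two Japan items concern consent below age 20 and recording of deviations. Neither concerns hepatitis B.

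**The concern.** Two statements in one section cannot both be followed by a site under a local mandate. The text tells it to repeat HBV DNA every 12 weeks; the table says HBV DNA is done once.

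The places a coordinator or laboratory would consult for what to draw at a given visit are silent after Screening. The text also does not say from which visit the 12 weeks are counted.

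The subjects concerned are those whose antibody results are the reason for the rule. Under section 3.12, a subject positive for core antibody can enter on one undetectable HBV DNA result at Screening. The last study drug administration is at Week 40, and Protocol section 2.2 describes the drug as one that may impair immune function. What is at stake is a conditional safety test that could be overlooked, or done at times the schedule does not name. No efficacy result is involved.

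**Working it through.** No power, alpha or event figure is involved, so the check is a side-by-side reading followed by a count of days.

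**Step 1. Do the statements conflict?**

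| Place | HBV DNA after Screening |
|---|---|
| 3.12, Hepatitis B and C Testing | Every 12 weeks, where locally mandated, in defined antibody-positive subjects |
| 3.12, laboratory table, footnote d | None; no exception stated |
| 2.1 and 2.2, visit lists | Not named at any visit after Screening |
| Appendix D | No hepatitis tick after Day 0 |
| 5.2, country-specific | Not mentioned |

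Without a local mandate the rows agree. Under a mandate the first row conflicts with the second and finds no place in the others.

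**Step 2. Is the footnote only shorthand that leaves conditional tests aside?** The same set of notes states conditions where they apply. INR is tied to raised transaminases, and serum pregnancy testing after Screening is tied to a positive urine test. The TB row, which is repeated at Week 52, does not carry superscript d, while the hepatitis and HIV rows do. So d is used to mark tests done once, and HBV DNA is marked that way without qualification.

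**Step 3. How many tests are implied?** The interval is 12 × 7 = 84 days and Week 52 is Day 365. 365 / 84 = 4.3, so four complete intervals fit when counted from Day 0. The visit lists show 0 tests over the same time.

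**Step 4. Do existing blood draws already supply the rhythm?** Central-laboratory draws after Baseline are on Days 14, 28, 70, 112, 140, 196, 280 and 365. Due dates are the starting day plus 84, 168, 252 and 336.

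| Count starts at | Due days | Days to nearest draw |
|---|---|---|
| Screening, Day -35 | 49, 133, 217, 301 | 21, 7, 21, 21 |
| Screening, Day -1 | 83, 167, 251, 335 | 13, 27, 29, 30 |
| Day 0 | 84, 168, 252, 336 | 14, 28, 28, 29 |
| Week 4, Day 28 | 112, 196, 280, 364 | 0, 0, 0, 1 |

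Visit windows are ±3 days up to Week 16 and ±7 days from Week 20.

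- **From Day 0:** no due date falls within a window of a draw. Day 168 is the Week 24 visit, which has no laboratory list.
- **From Screening:** whatever the screening day, the third due date lies between Day 217 (-35 + 252) and Day 251 (-1 + 252). The draws on either side are Days 196 and 280, so it is at least 217 - 196 = 21 days from a draw.
- **From Week 4:** the count matches Weeks 16, 28, 40 and 52, with gaps of 84, 84, 84 and 85 days.

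Existing visits could therefore carry 12-weekly sampling, but only from a starting point that the documents do not name.

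**Step 5. How many subjects?** This cannot be computed. The documents give neither antibody prevalence nor a list of sites under a mandate.

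**The case against.** The case on the other side is substantial, and much of it stands.

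- **The rule is conditional.** It applies only under a local mandate, and the documents do not say whether any planned country (United States, Canada, Japan, Australia) has one. The silence of the Japan items is equally consistent with none applying there. This stands, and it means the number affected could be zero.
- **The table may describe only the screening algorithm.** The row sits under infection screening and is labelled quantitative, which matches the step at Screening where HBV DNA is quantified after a positive core antibody. The 12-weekly sentence could then be a separate local provision. That is a fair reading, but it leaves the repeat test with no table row at all, so the gap remains.
- **Absence from the visit lists is weak evidence alone.** INR, also conditional, is missing from them too. This stands; the point rests on the unqualified footnote, and the lists only support it.
- **Some evidence is incomplete.** Operations Manual Figure 1, on managing hepatitis B serology, is not shown and might address follow-up testing. The ticks in the available text of Appendix D are unreliable: the ECG row lacks Week 52, although section 2.2 lists an ECG there. The hepatitis row shows a Day 0 tick that the Baseline list does not repeat.
- **Sites have other routes.** Section 3.16 allows blood for tests listed in 3.12 at unscheduled safety visits, at the investigator's discretion. This permits a sample but does not schedule one.

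Three stronger readings are tempting. A reader might infer that sites would miss the monitoring; the documents support only that they could, since the text and the local mandate still instruct them. A reader might infer that laboratory kits would lack the tube and deviations would follow; that depends on laboratory instructions not included here. A reader might infer that the visit schedule cannot hold a 12-week rhythm because there is no Week 12 visit; Weeks 16, 28, 40 and 52 are 12 weeks apart and all have central-laboratory draws. What is missing is the starting visit.

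**Conclusion.** The inconsistency is real and limited. Within Operations Manual 3.12, an unqualified once-only footnote contradicts a conditional instruction to repeat the same test, no visit list after Screening names it, and the start of the 12-week count is not stated. A covered site or laboratory working from the table and visit lists could overlook the monitoring.

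The size is about four repeat tests per covered subject by Week 52 in the text, against none in the visit lists. The number of covered subjects is unknown and may be zero.

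The conclusion assumes that the fourth table note is footnote d, which the order of the notes and the rows carrying each superscript support. It also assumes that Figure 1 does not resolve the conflict. Even if the figure does, the footnote as worded would still need correcting. This is a safety-schedule inconsistency with no bearing on sample size, multiplicity or the primary analysis.

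**What to change.** Reconcile the Hepatitis B and C Testing text and the laboratory table in Operations Manual 3.12, the visit lists in 2.1 and 2.2, Protocol Appendix D and, if it touches the matter, Figure 1, so that all state the same rule. Which rule applies is for the sponsor's medical team to decide.

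- **If the locally mandated testing is kept:** add the exception to footnote d, say whether the table's quantitative row is the assay meant, and add a conditional line to Appendix D and the visit lists naming the existing visits at which the sample is drawn. Naming the visits also settles where the 12-week count starts. Section 5.2 could state in which countries the mandate applies.
- **If it is not kept:** remove the repeat-testing sentences, and the footnote can stand.

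The cost is wording in the Operations Manual and Appendix D. If the testing is kept, it may also need one extra tube at existing blood draws in covered subjects. No change to the SAP is needed.
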